6.1 Inclusion criteria

Subjects must meet all of the following inclusion criteria to be included in the study:

1. Written informed consent signed before any study-specific procedure
2. Men or women aged 18 years and older. The lower age limit may be higher if legally required in the participating country.
3. Women of childbearing potential can only be included in the study if a pregnancy test is negative at the screening visit and if they agree to use adequate contraception. Adequate contraception is defined as any combination of at least 2 effective methods of birth control, of which at least one is a physical barrier (e.g. condoms with hormonal contraception or implants or combined oral contraceptives, certain intrauterine devices). Women are considered post-menopausal and not of child-bearing potential if they have had 12 months of natural (spontaneous) amenorrhea with an appropriate clinical profile (e.g. age appropriate) or 6 months of spontaneous amenorrhea with serum FSH levels > 40 mIU/mL [for US only: FSH levels > 40 mIU/mL and estradiol < 20 pg/mL] or have had surgical treatment such as bilateral tubal ligation, bilateral ovariectomy, or hysterectomy.
4. Subjects with **type 2 diabetes mellitus** as defined by the American Diabetes Association (35)
5. Subjects with a clinical diagnosis of DKD based on either of the following criteria at the Run-in and Screening Visit:
 - Persistent **high albuminuria** defined as UACR of ≥ 30 mg/g (≥ 3.4 mg/mmol) but < 300 mg/g (< 33.9 mg/mmol) in 2 out of 3 first morning void samples and eGFR ≥ 25 but ≤ 90 mL/min/1.73 m² (CKD-EPI) (36, 37)⁴
 - OR
 - Persistent **very high albuminuria** defined as UACR of ≥ 300 mg/g (≥ 33.9 mg/mmol) in 2 out of 3 first morning void samples and eGFR ≥ 60 mL/min/1.73 m² (CKD-EPI) (36, 37)

Note: One re-assessment of eGFR and UACR is allowed at the Run-in Visit and the Screening Visit. If one of the 3 UACR measurements is missing but the other 2 are valid, these values can be used to assess subject's eligibility for this study.
6. Prior treatment with ACEIs and ARBs as follows:
 - For at least 4 weeks prior to the Run-in Visit, subjects should be treated with *either* an ACEI or ARB, *or* both
 - Starting with the Run-in Visit, subjects should be treated with only an ACEI or ARB

⁴ **Note:** The number of subjects with eGFR ≥ 60 and high albuminuria will be capped at approximately 10% of the total population with high albuminuria at screening.

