10.3.4.2 Laboratory data

The number of subjects with treatment emergent (until 3 days after any temporary or permanent interruption of study drug) abnormal laboratory values above or below the normal range will be tabulated by the laboratory parameter and treatment group.

Summary statistics including changes to baseline will be calculated by treatment group and visit for all quantitative laboratory parameters, e.g. for hematology, HBA1c, clinical chemistry and urinalysis. Geometric statistics and ratios to baseline will be presented for creatinine instead of arithmetic statistics with changes from baseline. For eGFR the relative change will be displayed in addition to the absolute change from baseline.

Summary statistics for serum potassium, eGFR and serum creatinine will also be repeated by treatment group and visit separately for each level of the stratification factors (type of albuminuria, region and eGFR category, history of CVD).

The following special safety parameters will be further assessed by displaying the number of subjects with safety events as described below by treatment group, visit and for any time on treatment (including unscheduled assessments) and up to 3 days after last study drug administration. This will also be performed by stratification factors. The summaries will be performed for the number of subjects with

- Absolute value of serum potassium >5.5 mmol/L and >6 mmol/L
- Relative decrease from baseline in eGFR of $\geq 30\%$, $\geq 40\%$, $\geq 50\%$ and $\geq 57\%$, also sustained decrease over 4 weeks
- Absolute value of eGFR < 30 mL/min/1.73m².

The percentage of subjects with the respective events (non-stratified) at any time post-baseline (including unscheduled assessments) and within 3 days after last study drug administration will be compared between the finerenone and the placebo treatment group by applying separate explorative χ^2 tests with continuity correction. If the expected number of subjects in at least 1 cell of the 2x2 contingency table is <5 (50), Fisher's exact test will be applied instead of the χ^2 test. Estimates and two-sided 95% confidence intervals will be provided for each treatment group and the treatment differences. Clopper Pearson confidence intervals will be calculated for each treatment group, while for treatment differences the exact unconditional confidence limits will be calculated.

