4.5.3 Other data handling

Only the data provided by the central laboratory will be used for analysis, values from local laboratories will not be used in the statistical analysis and will be listed only unless there are no values from the central laboratory available for baseline.

In case of retests for Run-in and Screening visits, the closest measurement prior to randomization will be used for analysis instead of the scheduled measurements. At all visits starting at Visit 1 and if not stated otherwise, only the values at scheduled measurements will

be used for analysis. In the unexpected case that more values than planned are available for a scheduled visit, only the first valid value will be used.

For the derived visit “Any time post-baseline” (applicable for efficacy) this will include any measurement after date of randomization, including unscheduled assessments. For the derived visit “Any treatment-emergent” (applicable for safety), only assessments on or after study medication start date until 3 days after the date of any temporary or permanent interruption of study drug, including unscheduled assessments, will be considered.

For those laboratory values which are <LLOQ (Lower limit of quantification), half the value of the LLOQ will be used for analysis. Differences between 2 values <LLOQ will be assigned values of 0. Ratios between 2 values <LLOQ will be assigned a value of 1. For values which are >ULOQ (Upper limit of quantification), the ULOQ will be used for analysis. This rule does not apply to the finerenone plasma concentration data.

In case of log-normally distributed data, descriptive statistics other than minimum, maximum and median will only be calculated if at least 2/3 of the individual data were measured and were above the lower limit of quantification. In tables showing descriptive statistics, where values below LLOQ are included, these descriptive statistics will be marked.

Urinalysis is assessed 3 times per visit. UACR will be determined 3 times at each visit from first morning void urine samples collected on 3 consecutive days. For the analyses of UACR, the 3 measurements at one visit will be combined provided that at least 2 measurements are available. First, the coefficient of variation (CV) will be calculated for the 3 values as follows considering the log-normal distribution for UACR [7]:

$$CV = \sqrt{\exp(SD_{\ln}^2) - 1},$$

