- Ethnicity (hispanic or latino, not hispanic or latino, not reported)
- Baseline BMI (<20 , 20 to <25 , 25 to <30 , 30 to <35 , ≥ 35 kg/m²)
- Baseline weight (<60 , 60 to <90 , ≥ 90 kg)
- eGFR category at baseline (eGFR <30 , 30 to <60 , 60 to <90 and ≥ 90 mL/min/1.73m²)
- eGFR at baseline 25 to <45 ml/min/1.73m² and baseline serum potassium value >4.5 mmol/L (yes, no)
- ACEI at baseline (yes, no)
- ARB at baseline (yes, no)
- Beta-blocker at baseline (yes, no)
- Diuretic at baseline (yes, no)
- Statins at baseline (yes, no)
- Other anti-diabetic treatment at baseline: insulin and analogues (yes, no); DPP-4 inhibitors (yes, no); biguanides (yes, no); sulfonylureas (yes, no); alpha glucosidase inhibitors (yes, no); meglitinides (yes, no); thiazolidinediones (yes, no)
- Potassium supplementation at baseline (yes, no)
- Potassium lowering agents (including binders) at baseline (yes, no)
- Potency of concomitant CYP3A4 inhibitor medication at baseline (strong, unclassified, moderate, weak, none)
- Potency of concomitant CYP3A4 inducer medication at baseline (strong, unclassified, moderate, weak, none)
- Baseline waist circumference (normal [men <94 cm, women <80 cm], increased [men 94 - 102 cm, women 80 - 88 cm], substantially increased [men >102 cm, women >88 cm])

If the result for a subgroup cannot be calculated due to a small sample size or number of events, then this subgroup will be dropped.

Individual country analyses, e.g. for Japan, required for regulatory purposes, will be included in a country-specific study SAP.

For the safety variables

- Number of subjects with hyperkalemia (treatment-emergent only)
- Number of subjects with hospitalization for hyperkalemia
- Number of subjects discontinuing study drug permanently due to hyperkalemia
- Number of subjects with hospitalization for worsening of renal function
- Number of subjects discontinuing study drug permanently due to worsening of renal function

exploratory subgroup analyses will be performed in the following selected subgroups:

- eGFR category at baseline (eGFR <25, 25 to <45, 45 to <60 and ≥ 60 mL/min/1.73m²)
- eGFR category at baseline (eGFR <30, 30 to <60, 60 to <90 and ≥ 90 mL/min/1.73m²)
- Baseline serum potassium value (≤ 4.5 , > 4.5 mmol/L)
- Baseline serum potassium value (≤ 4.8 mmol/L, > 4.8 to 5.0 mmol/L, > 5.0 mmol/L)
- Hyperkalemia (based on MLG) in medical history (yes, no)

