6.4.2 Laboratory parameters

The number of subjects with treatment-emergent (until 3 days after any temporary or permanent interruption of study drug) abnormal laboratory values above or below the normal range will be tabulated by the laboratory parameter and treatment group.

Summary statistics including changes to baseline will be calculated by treatment group and visit for all quantitative laboratory parameters, e.g. for hematology, HbA1c, clinical chemistry and urinalysis. Geometric statistics and ratios to baseline will be presented for creatinine and UACR instead of arithmetic statistics with changes from baseline. For eGFR the relative change will be displayed in addition to the absolute change from baseline.

Summary statistics for serum potassium, eGFR and serum creatinine will also be repeated by treatment group and visit separately for the following subgroups:

- eGFR category at baseline (eGFR <30, 30 to <60, 60 to <90 and ≥ 90 mL/min/1.73m²)
- Baseline serum potassium value (≤ 4.8 mmol/L, >4.8 to 5.0 mmol/L, >5.0 mmol/L)

The following special safety parameters will be further assessed by displaying the number of subjects with treatment-emergent safety events. This will also be performed by visit and by stratification factors. The summaries will be performed for the number of subjects with:

- Absolute value of serum potassium >5.5 mmol/L and >6.0 mmol/L,
- Relative decrease from baseline in eGFR of $\geq 30\%$, $\geq 40\%$, $\geq 50\%$ and $\geq 57\%$
- Absolute value of eGFR <30 mL/min/1.73m².

The percentage of subjects with the respective treatment-emergent events (non-stratified) will be compared between the finerenone and the placebo or active control group by applying separate explorative χ^2 tests with continuity correction. If the expected number of subjects in at least 1 cell of the 2x2 contingency table is less than 5 (see reference 5), Fisher's exact test will be applied instead of the χ^2 test. Estimates and two-sided 95% confidence intervals will be provided for each treatment group and the treatment differences. Clopper Pearson confidence intervals will be calculated for each treatment group, while for treatment differences, due to the computational burden of exact unconditional confidence limits, the Wald asymptotic confidence limits will be calculated.

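### The treatment-emergent eGFR <30 count in SAP 6.4.2 has no baseline condition, so subjects who enter at 25–29 and do not change are counted as events in both arms

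*SAP*

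**What the plan says.** SAP 6.4.2 assesses special safety parameters by "displaying the number of subjects with treatment-emergent safety events", and one of them is "Absolute value of eGFR <30 mL/min/1.73m²". The counts are shown by visit and by stratification factor. The unstratified percentages are compared by an explorative chi-square test with continuity correction (Fisher's exact test if an expected count is below 5), with confidence intervals for each arm and for the difference.

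Treatment-emergent is defined by time alone. SAP 4.5.3 admits "only assessments on or after study medication start date until 3 days after the date of any temporary or permanent interruption of study drug", unscheduled values included. SAP 6.4.2 applies the same window to "treatment-emergent (until 3 days after any temporary or permanent interruption of study drug) abnormal laboratory values". Neither text asks for a baseline value of at least 30, a fall from baseline or a second reading.

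For high albuminuria, Protocol 6.1 requires "eGFR ≥ 25 but ≤ 90 mL/min/1.73 m²". For very high albuminuria it requires UACR ≥300 mg/g "in 2 out of 3 first morning void samples and eGFR ≥ 60 mL/min/1.73 m²", so only the first group can be eligible at 25–29. The SAP foresees subjects who start below 30: its subgroup list (4.5.4) contains "eGFR category at baseline (eGFR <30 , 30 to <60 , 60 to <90" as baseline categories.

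Protocol 10.3.4.2 has the same absolute eGFR item. To the relative decreases (≥30%, ≥40%, ≥50%, ≥57%) it adds "also sustained decrease over 4 weeks". SAP 6.4.2 lists these decreases without that addition, and the change history in SAP Section 7 does not mention its removal.

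**The concern.** A treatment-emergent count is normally read as something that appeared or worsened on treatment; SAP 6.4.1 defines treatment-emergent adverse events in that way. Here the threshold lies inside the eligible range, so part of the count is settled at entry. The neighbouring items differ. The relative eGFR decreases refer to baseline, and the potassium thresholds of 5.5 and 6.0 mmol/L lie above the entry limit of 4.8.

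Subjects already below 30 carry no information on new renal harm in this item, yet they enter numerator and denominator in both arms. A real excess of new eGFR <30 would then look smaller in relative terms and be harder to detect. In a safety comparison that is the unwelcome direction, and Protocol 3.3 names worsening renal function as a main risk of steroidal MRAs that is not ruled out for finerenone.

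**Working it through.** The plan states no expected rate for this item and no share of subjects at 25–29, so there is no figure to reproduce. The check has four steps.

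**1. Definition against entry.** The entry floor is 25 and the threshold is 30. With no baseline condition, an eligible subject at 25–29 with unchanged eGFR meets the definition at the first on-treatment sample. Leaving out the pre-dose Day 1 sample does not help, because later unchanged values also fall below 30.

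**2. Can a planned table separate these subjects?** The eGFR stratification levels are 25 to <45, 45 to <60 and ≥60, and the lowest mixes 25–29 with 30–44. The baseline <30 category in SAP 6.4.2 applies to summary statistics of potassium, eGFR and creatinine, not to this count.

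**3. Contribution to each arm's percentage.** Contribution = w × b × c, where
- w = share of the safety set in the 25 to <45 stratum: 15–30%, assumed;
- b = share of that stratum with baseline <30: about 21%;
- c = share of those with at least one on-treatment value <30: 95–98%.

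The values of b and c come from a simulation under assumptions that are not in the documents: true eGFR uniform from 15 to 60 and constant; entry if Run-in ≥25 and Screening 25 to <45; within-subject SD 2, 3 or 4 mL/min; 10 post-baseline values. Baseline <30 came out at 20.9%, 20.4% and 21.0%.

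- Low end: 0.15 × 0.21 × 0.95 = 0.030
- High end: 0.30 × 0.21 × 0.98 = 0.062

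This is about 3–6 percentage points per arm.

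**4. Effect on the comparison.** Let s be the share of the whole safety set with baseline <30, all of them counted, and p the incidence of eGFR <30 among subjects with baseline ≥30. The observed proportion is s + (1 − s)p, so the observed risk difference is (1 − s)(p₁ − p₀). For illustration, assume p₀ = 6% (placebo), p₁ = 8% (finerenone; true risk ratio 1.33) and 3,700 per arm (approximately 7,400 in SAP Section 3, randomized 1:1). Approximate power is Φ(d/√{[P₀(1 − P₀) + P₁(1 − P₁)]/n} − 1.96), where P₀ and P₁ are the proportions compared and d is their difference.

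Example with s = 5%:
- placebo 0.05 + 0.95 × 0.06 = 0.107; finerenone 0.05 + 0.95 × 0.08 = 0.126
- risk ratio 0.126/0.107 = 1.18; risk difference 0.95 × 2.0 = 1.9 points
- power Φ(0.019/0.00746 − 1.96) = Φ(0.59) = 72%
- restricted to baseline ≥30 (n = 3,515): Φ(0.020/0.00608 − 1.96) = Φ(1.33) = 91%

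| s | Baseline <30 per arm | Observed placebo / finerenone | Risk ratio | Risk difference (points) | Power as planned | Power if baseline ≥30 |
|---|---|---|---|---|---|---|
| 1% | 37 | 6.94% / 8.92% | 1.29 | 1.98 | 88% | 92% |
| 2% | 74 | 7.88% / 9.84% | 1.25 | 1.96 | 84% | 92% |
| 5% | 185 | 10.7% / 12.6% | 1.18 | 1.90 | 72% | 91% |
| 10% | 370 | 15.4% / 17.2% | 1.12 | 1.80 | 55% | 89% |

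The formula ignores the continuity correction, so the powers serve for comparison with each other only.

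**Single readings.** A second simulation (constant true eGFR, within-subject CV 5–10%, 6 or 11 visits, all assumed) shows what confirmation would add. The chance of at least one reading <30 is 0.83–0.99 at a true value of 31 and 0.16–0.87 at 33. With two consecutive readings it is 0.25–0.69 and 0.004–0.23. At a true value of 29, two consecutive readings <30 still occur with probability 0.85–1.00. Confirmation therefore reduces noise near the line but cannot replace the baseline condition.

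**The case against.** The case for leaving the item alone is substantial.

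- **It follows the protocol.** Protocol 10.3.4.2 has the same absolute item, and its sustained wording belongs to the relative decreases only. The label says absolute value, not new or worsening. This stands: the SAP does not depart from the protocol on eGFR <30. Both documents share the weakness.
- **The contrast is not biased toward an arm.** Randomization makes the automatic counts non-differential in expectation, the test is explorative, and SAP 4.4 sets no predefined stopping conditions for safety monitoring. This stands too. The effect is dilution of the ratio and the test; the risk difference that the SAP reports is little affected.
- **Renal harm is measured elsewhere.** The same list has baseline-referenced decreases. eGFR is summarized by baseline category with <30 as its own row. Hospitalization and permanent discontinuation for worsening renal function are analysed by baseline eGFR (SAP 4.5.4), and there are mixed-model and slope analyses (6.2.3.3). The number with baseline <30 in each arm will appear among the baseline characteristics (6.1.2). This limits the importance but leaves the row itself hard to interpret.
- **Confirmation can lose real events.** The window closes 3 days after any interruption. A subject whose eGFR falls below 30 and whose drug is then interrupted may have no second value inside it. This is right, and it is why a confirmed version should only supplement the count.

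Two stronger readings are tempting. A reader might take the simulated any-visit rate in the lowest stratum (37–50%) and conclude that 6–15 points of the whole safety set are spurious (0.15 × 37% to 0.30 × 50%). That sum includes subjects with baseline ≥30 who cross the line by measurement noise; those with baseline <30 supply only 40–55% of it. A reader might also infer that the plan has no confirmed renal analysis. It has: sustained decreases of ≥40% and ≥57% and sustained eGFR <15 are time-to-event variables in SAP 6.2.3.

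**Conclusion.** The point holds as a reporting weakness in one safety row. Stable subjects who start at 25–29 are counted as treatment-emergent events, and no planned table takes them out.

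The size is not documented. Under the assumed shares in step 3, these subjects contribute about 3–6 percentage points to each arm. With the illustrative 6% against 8%, shares of 3% and 6% would lower the observed risk ratio from 1.33 to 1.22 (10.76%/8.82%) and 1.16 (13.52%/11.64%). The risk difference would fall only from 2.0 to 1.94 and 1.88 points. If few subjects enter below 30, the effect is small.

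The documents do not support reading this as bias in favour of finerenone or as concealment of renal harm. The primary analysis and the sample size are unaffected.

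The missing sustained version of the relative decreases is a separate discrepancy between protocol and SAP. Because sustained ≥40% and ≥57% exist as efficacy variables, what is lost is mainly sustained ≥30% and ≥50%, and the treatment-emergent version in the safety set.

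**What to change.** In SAP 6.4.2:

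1. Count treatment-emergent eGFR <30 among subjects with baseline eGFR ≥30, with those subjects as the denominator for the percentages, the test and the confidence intervals. Show subjects with baseline <30 in a separate row.
2. As a supplement, not a replacement, add a version that requires a second value <30 at least 4 weeks after the first. Let the confirming value fall after a drug interruption, so that falls followed by interruption are not lost.
3. Separately, reconcile the section with Protocol 10.3.4.2 by restoring the sustained (4-week) version of the ≥30%, ≥40%, ≥50% and ≥57% decreases, or record why it was dropped.

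The cost is SAP wording, a filter and some table rows, with no new data collection. The denominator becomes slightly smaller, and some late events will have no confirming value.

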7.3 Treatment assignment - amended

This section was changed in Amendment 3, see Section 15.1.2.8.

Eligible subjects will be randomized within ≤ 2 weeks after the Screening Visit. The randomization will be stratified by region (North America, Europe, Asia, Latin America and others), type of albuminuria at screening (high or very high albuminuria) and eGFR at screening (25 to <45 , 45 to <60 , ≥ 60 mL/min/1.73m²) and history of CVD (present, absent; see definition of CVD in Table 16–5). The eGFR will be calculated by the Central Laboratory applying the CKD-EPI formula (36).

The number of subjects with high albuminuria and eGFR ≥ 60 mL/min/1.73 m² will be capped at approximately 10% of the total population with high albuminuria at screening. The number of subjects with high albuminuria and without a history of CVD will be capped at approximately 40% of the total population with high albuminuria at screening.

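### The explorative comparison of treatment-emergent eGFR <30 pools over the eGFR strata used in randomization, so its test is conservative and its interval somewhat wide

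*SAP*

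**What the plan says.** SAP 6.4.2 lists seven thresholds as special safety parameters: potassium >5.5 and >6.0 mmol/L, relative eGFR declines of at least 30, 40, 50 and 57%, and an absolute eGFR below 30 mL/min/1.73m². For all of them, "The percentage of subjects with the respective treatment-emergent events (non-stratified) will be compared between the finerenone and the placebo or active control group", using chi-square "tests with continuity correction" and Fisher's exact test when an expected count is below 5. "Estimates and two-sided 95% confidence intervals will be provided for each treatment group and the treatment differences"; for the differences, "the Wald asymptotic confidence limits will be calculated".

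Protocol 10.3.4.2 plans the same unstratified comparison: the percentages "will be compared between the finerenone and the placebo treatment group by applying separate explorative" chi-square tests. It differs in giving exact unconditional limits for the difference. SAP 7.3 records the change to Wald limits and gives computational burden as the reason. Neither document says why the strata are left out.

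Protocol 7.3 states: "The randomization will be stratified by region (North America, Europe, Asia, Latin America and others), type of albuminuria at screening". The eGFR categories are 25 to <45, 45 to <60 and ≥60, and history of CVD is the fourth factor. SAP 6.4.2 also shows the event counts by stratum: "This will also be performed by visit and by stratification factors".

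**The concern.** When allocation is balanced within strata, chance imbalance between the arms in those strata is largely removed. A variance computed from the pooled 2×2 table still counts it. If a stratum predicts the event strongly, the pooled standard error is too large, the nominal 5% test rejects less than 5% of the time under the null, and the nominal 95% interval covers more than 95%.

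Absolute eGFR <30 is the listed event most exposed to this. Protocol 6.1 admits patients from eGFR 25, and SAP 6.4.2 states no exclusion for those already below 30 at baseline, so they can count from their first on-treatment value. A patient who enters at 60 or above must lose more than half of eGFR to count. For a safety event a conservative test errs towards missing a harm, and Protocol 3.3 names worsening of renal function as a main risk of the drug class that is not ruled out for finerenone.

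**Working it through.** **Plan figures.** The documents give no precision or power figure for this comparison, so there is none to reproduce. The inputs they do give are 1:1 allocation (Protocol 5), about 7400 randomized (SAP 3), hence n ≈ 3700 per arm (the safety set slightly fewer), and the strata (Protocol 7.3).

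**Assumptions.** The documents give neither stratum risks nor stratum shares.
- Shares: 50% of patients have very high albuminuria (range 40–60%). By Protocol 6.1 they all have eGFR ≥60. Of the high-albuminuria group, 10% have eGFR ≥60 (the cap in Protocol 7.3), and the rest are split evenly over the two lower categories. At 50% the shares are 0.225 / 0.225 / 0.55.
- Risks of eGFR <30 by category: four scenarios, tabulated below.
- Allocation is exactly balanced within eGFR category.

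**Formulas.** With shares w_k, risks p_k and p̄ = Σ w_k p_k:
- pooled variance U = p̄(1 − p̄)
- within-stratum variance S = Σ w_k p_k(1 − p_k)
- standard-error ratio r = √(U/S)
- 95% half-width = 1.96·√(2V/n), with V = U or S
- actual size of the nominal 5% test ≈ 2·(1 − Φ(1.96 r)), slightly less with the continuity correction

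**Worked case, 45/7/1%.**
- p̄ = 0.225·0.45 + 0.225·0.07 + 0.55·0.01 = 0.1225
- U = 0.1225·0.8775 = 0.1075
- S = 0.225·0.2475 + 0.225·0.0651 + 0.55·0.0099 = 0.0758
- r = √(0.1075/0.0758) = 1.19. The strata explain 1 − S/U = 29.5% of the variance.
- Half-widths: 1.96·√(2·0.1075/3700) = 1.49 percentage points pooled, 1.96·√(2·0.0758/3700) = 1.25 stratified
- Size ≈ 2·(1 − Φ(2.33)) = 2.0%; about 1.8% in simulation with the continuity correction

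**All scenarios at the 50% share.** Size and power are from simulated trials with allocation balanced within eGFR category. Power is for a risk ratio of 1.12, planned test against Cochran-Mantel-Haenszel (CMH).

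| Risks | SE ratio r | Half-width, pooled → stratified (pp) | Size of planned test | Power, planned vs CMH |
|---|---|---|---|---|
| 10/5/2% | 1.01 | 0.94 → 0.93 | about 4% | 18% vs 20% |
| 30/8/2% | 1.08 | 1.35 → 1.24 | about 3% | 35% vs 43% |
| 45/7/1% | 1.19 | 1.49 → 1.25 | about 1.8% | 45% vs 63% |
| 60/4/0.5% | 1.38 | 1.61 → 1.17 | about 0.6% | 55% vs 85% |

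The CMH test holds its size at about 5% throughout. Coverage of the planned interval is about 95%, 96%, 98% and 99% in the four rows. Moving the very-high-albuminuria share from 40 to 60% changes r little: 1.18 to 1.20 in the third row and 1.37 to 1.40 in the fourth.

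**Second check with other shares**, from 20/20/60 to 50/30/20. Stratifying narrows the interval by about 1% for 10/5/2%, 5–8% for 30/8/2%, 11–15% for 50/12/3% and 22–27% for 70/15/2%. The excess half-width runs from 0.01 to about 0.5 percentage points.

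**Events with little gradient.** With risks of 20/18/15%, as might hold for a relative eGFR decline, the excess is about 0.01 percentage points or less.

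**The case against.** The case for leaving the text alone is substantial. The tests are explorative, carry no decision rule, and err on the conservative side. The crude difference is unbiased. The counts are shown by stratification factor, so the 25 to <45 category can be read by arm. Renal effects are also analysed with the strata elsewhere: the renal composites and sustained declines by stratified log-rank and Cox models (SAP 6.2.2.1, 6.2.3.1), and eGFR change and slopes by models with the stratification factors (SAP 6.2.3.3). The DMC sees unblinded safety data.

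All of this stands and limits the consequence. It does not remove the point, because none of these gives a stratified estimate or test of eGFR <30 itself.

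A reader might go further and infer four things that the documents do not support:
- **The intervals are far too wide.** No stratum risk is stated, and a weak gradient gives an excess of only about 1%.
- **The safety comparisons in general are affected.** Only one of the seven thresholds is tied this closely to the eGFR stratum.
- **The Wald limits are to blame.** The protocol's exact limits were also unstratified; the cause is pooling over strata.
- **A renal harm would be hidden.** The stratified renal analyses and the by-stratum counts argue against that.

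**Conclusion.** The point holds for eGFR <30 alone. The direction is certain if the screening eGFR category predicts the event, which entry down to eGFR 25 makes likely. The size is not known. Under the assumed risks the standard error is between about 1% and about 40% too large, the excess half-width is about 0.01 to 0.5 percentage points, and the loss of power at a risk ratio of 1.12 is about 2 points in the weak case, 8 in the moderate and 18 in the 45/7/1% case. A steeper gradient would give more, but nothing in the documents places the trial within this range. For the potassium and relative-decline thresholds the effect is expected to be negligible. This is a free improvement, since the trial already randomizes by these groups. It is of minor priority because the tests are explorative.

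**What to change.** In SAP 6.4.2, for absolute eGFR <30, replace the pooled test and interval by a CMH test and a Mantel-Haenszel common risk difference with a stratified 95% CI. Stratify by screening eGFR category and type of albuminuria. Under the entry criteria these form only four cells, since very high albuminuria requires eGFR ≥60. With 1:1 allocation the Mantel-Haenszel weights are proportional to stratum size, so the estimate targets the same average difference as the crude one. Keep the crude percentages with Clopper-Pearson limits as description, and leave the other six thresholds as planned.

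The cost is one sentence and a standard SAS option. SAP 4.1 already defines the strata, and no new data are needed. The same edit can remove the reference to an active control group, which this placebo-controlled trial does not have.
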